2.2 Secondary Objectives

The secondary objectives of this study are to:

- a) To examine the ORR, CR rate, and prognostic relevance of FDG-PET following 2 cycles of SGN-35.
- b) To evaluate the safety of sequential SGN-35/AVD/SGN-35 therapy.
- c) To determine the 2-year progression-free survival (PFS), time to treatment failure (TTF), freedom from progression (FFP), and overall survival (OS) rates following SGN-35/AVD sequential therapy.
- d) To evaluate patient-reported outcomes at baseline and during treatment to determine potential symptom palliation (of baseline/pre-treatment symptoms), treatment-related symptoms, and overall health-related quality of life (HRQL).
- e) To examine the association between baseline and end-of-treatment patient co-morbidities as assessed by the Cumulative Illness Rating Scale (CIRS) with outcome (CR, TTF, FFP, PFS, and OS) and toxicity.
- f) To collect peripheral blood for proposed future studies of tumor and host characteristics that may predict for clinical outcome and enhance existing prognostic indices.

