5 TREATMENT PLAN

5.1 Overall description.

Therapy on this protocol is divided into 3 phases: 1) SGN-35 “lead in” as a single-agent for 2 cycles/doses (1.8 mg/kg q 3 weeks x 2 doses); 2) AVD chemotherapy for 6 cycles; and 3) SGN-35 consolidation with SGN-35 given as a single-agent once every 3 weeks for 4 total doses (see Figure 2).

Figure 2. Trial schema.

* Any patient who has not achieved a CR or PR after 6 cycles of AVD should be taken off study and not proceed with SGN35 consolidation therapy; however patients who do not complete 6 cycles of AVD (due to toxicity: designated ‘chemotherapy intolerant’), but have achieved PR or CR may proceed with SGN35 consolidation therapy.

5.2 SGN-35 “lead in”.

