• Hematologic	
 Continue at same dose level. 	
 Continue at same dose level. 	
 Withhold dose until toxicity is \leq Grade 2, or has returned to baseline, then resume treatment at the same dose level.^b Consider growth factor support (eg, G-CSF) for treatment of neutropenia and prophylaxis in subsequent cycles. 	
 Withhold dose until toxicity is \leq Grade 2, then resume treatment at the same dose level. Consider growth factor support (eg, G-CSF) for treatment of neutropenia and prophylaxis in subsequent cycles. For the second occurrence of Grade 4 toxicity (if neutropenia, while receiving growth factor support), withhold dose until toxicity is \leq Grade 2, then reduce the dose to 1.2 mg/kg (or to 0.8 mg/kg if already on 1.2 mg/kg) and resume treatment^b

^a Patients who develop Grade 3 or 4 electrolyte laboratory abnormalities or nausea/vomiting that respond to treatment may continue study treatment without interruption.

^b Patients who develop Grade 3 or 4 lymphopenia may continue study treatment without interruption.

^c See Section 5.2.5.1 above regarding specific modifications for pancreatitis.

5.2.6 Treatment Compliance.

Subject compliance with treatment is anticipated to be well controlled for this trial as study treatment will be administered at the study site by the investigator or investigator designee. Treatment administration data will be captured and reviewed to ensure site compliance with the treatment regimen.

5.2.7 Other directions.

See **Section 8.1** for Preparation, Packaging and Labeling, and Concomitant Therapy and other information regarding SGN35.

5.2.8 Re-staging.

The first 22 evaluable patients entered onto the trial will have an “early” FDG-PET scan performed after the 2 ‘lead in’ cycles of SGN35. The recommended timing for this FDG-PET scan is to be completed between days 14 and 18 after the 2nd cycle of SGN35. See **Section 6.6** for further details regarding completion and interpretation of FDG-PET and see Table 3 Schedule of Activities in Section 7.0 for additional details.

5.2.8.1 Re-staging for evaluable patients 23 through 45.

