Patients 23 through 45 are not required to have a restaging PET or CT scan after the first 2 ‘lead in’ cycles of SGN35. PET and/or CT scans may be obtained at the investigators discretion at this time point. If there is documented progressive disease after SGN35 (i.e., prior to initiation of AVD), patients may still remain ‘on trial’ and proceed to AVD chemotherapy, however they will not receive SGN35 consolidation.

5.2.8.2 Re-staging for chemotherapy intolerant patients.

See Section 5.3.3.8 for this definition. Chemotherapy intolerant patients may proceed with consolidation SGN35 therapy if they have achieved either a PR or CR at time of chemotherapy intolerant designation. These patients should have repeat staging CT scans performed prior to initiation of SGN35 consolidation therapy (if not done within the preceding 30 days).

5.3 AVD chemotherapy.

5.3.1 Dosing.

Chemotherapy	Dose	Infusion	Timing
Doxorubicin (adriamycin)	25 mg/m ²	IV	Days 1 and 15
Vinblastine (velban)	6 mg/m ²	IV	Days 1 and 15
Dacarbazine	375 mg/m ²	IV	Days 1 and 15

(DTIC)			
--------	--	--	--

NOTE: A cycle is 28 days. Use actual weight to calculate body surface area. For further information regarding drug administration, please see Section 8.2.

5.3.2 Number of cycles.

Patients will receive 6 cycles of AVD chemotherapy, unless judged by the treating physician to be chemotherapy intolerant (see section 5.3.3.8). Each cycle is scheduled to be repeated every 28 days.

5.3.3 Dose modifications.

NOTE: All toxicities should be graded according to the CTC (version 4.0).

5.3.3.1 Hematologic Toxicity.

Dose delays and reductions of AVD chemotherapy only are to be done at the discretion of the treating physician and must be clearly documented on the Treatment eCRF in NOTIS along with the CTC (version 4.0) grade. Delays of greater than 3 weeks due to AVD toxicity must be approved by the PI and the QAM must be included on this correspondence. The following are only recommendations (are not mandatory) for modifications for AVD; SGN modifications are mandatory and are described above in Table 3. Some guidelines to be considered are for absolute neutrophil count of <500 on the day of treatment would be to consider addition of G-CSF (filgrastim) therapy. This is strongly preferred due to the long half-life of pegfilgrastim.

Patients with persistent severe neutropenia, especially despite use of granulocyte growth factor, could have reduction of doxorubicin and vinblastine by 25%.

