9. Combined PET/CT scan will be sufficient if the PET/CT is performed with oral contrast (intravenous contrast is encouraged, but not mandatory); if PET/CT is without oral contrast, then separate/dedicated CTs of chest/abdomen/pelvis (in addition to PET/CT) must be obtained. Please see Section 6.6 for further guidelines on recommended interpretation of PET scans.				
10. The first 22 evaluable patients entered on the study will have a repeat FDG-PET after the 2 "lead in" cycles of SGN35. This should be completed the week prior to planned initiation of AVD chemotherapy. All patients entered on study will have FDG-PET and CTs performed prior to day 1 of cycle 4 of AVD therapy (after day 15 of cycle 3). Thereafter, once a patient enters complete remission (CR), then only CT's (chest/abdomen/pelvis) should be obtained (not both PET/CT and dedicated CTs). All patients will have re-staging scans performed at the end of AVD chemotherapy (i.e., prior to start of SGN35 consolidation therapy).				
11. See Appendix III and Appendix IV for further details/methods for completion. This includes Co-morbidity assessment (Appendix III) and Activity of Daily Living (ADL) assessment (Appendix VI). Obtain once at baseline (pre-treatment) and then repeat once at the completion of all therapy.				
12. See Section 6.9 for exact timing and description and Appendix IV for Quality of Life forms.				
13. 30 days (+/- 2 days) after the last dose of treatment, patients should have repeat re-staging CTs +/- FDG-PET completed. Thereafter, the follow-up schedule will be office visits with blood tests q 3 months and re-staging CTs q 6 months for 3 years, then per local institutional guidelines. Patients who stop treatment early due to AEs or PD will also follow this schedule.				
14. See Table 4 in Section 12.3.3 for full explanation of which blood tubes (i.e., ACD/yellow, EDTA/purple, and red top) and timing (e.g., baseline/pre-SGN35, after 2 cycles of SGN35 lead-in, and after completion of AVD chemotherapy) of correlative blood studies.				

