- 9.3.3.4 The probability of stopping at the first stage is 0.07 if the true CR rate is 70% and is 0.67 if the true CR rate is 50%. With 45 evaluable patients, the probability of concluding this treatment is promising for further study is 0.9 and 0.1 assuming a true underlying CR rate of 70% and 50%, respectively. The maximum 90% two-stage confidence interval width for response is 0.26.
- 9.3.4 The incidence of overall response rate (CR and PR) and CR rate to induction SGN35 x 2 cycles will be reported for the initial 22 patients where PET is being employed. In exploratory analysis, outcome measures of PFS and OS will be analyzed for early responder vs non-responders at this timepoint. Patients will be dichotomized for CR/PR vs <PR and PET - vs. PET +.
- 9.3.5 We will also investigate time to progression free survival (PFS), defined as the time from registration to the earlier of disease progression or death from any cause without documentation of disease progression. The exponential Wald test will be used for the PFS analysis. With 45 evaluable patients, an accrual duration of 15 months and an additional follow-up duration of 3 years, there will be approximately 90% power to detect an

improvement in 2-year PFS rate from 45% (corresponding to median PFS 1.7 years) to 65% (corresponding to median PFS 3.2 years), using a one-sided type I error rate of 0.08. We assumed an exponential distribution for PFS and a uniform distribution for patient's entry to the study. The expected PFS event number would be about 20 at the time of analysis.

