9.8 Progression-Free Survival

9.8.1 Progression-free Survival (PFS) is defined as the time from entry onto study until lymphoma progression or death from any cause. PFS reflects tumor growth and, therefore, occurs prior to the endpoint of overall survival. In addition, PFS is not confounded by the administration of subsequent therapy. Whether a prolongation of PFS represents direct clinical benefit or a surrogate for clinical benefit depends on the magnitude of the effect and the risk-benefit ratio of the therapy under investigation. Unlike survival, the precise date of progression is generally unknown. It may be defined as the first date of documentation of a new lesion or enlargement of a previous lesion, or the date of the scheduled clinic visit immediately after radiologic assessment has been completed. Where there is missing information, censoring of the data may be defined as the last date at which progression status was adequately assessed or the first date of unscheduled new anti-lymphoma treatment.

9.9 Time to treatment failure.

9.9.1 Time to treatment failure (event-free survival) is measured from the time from study entry to any treatment failure including discontinuation of treatment for any reason, such as disease progression, toxicity, patient preference, initiation of new treatment without documented progression, or death.

9.4 Freedom from progression.

9.9.2 Freedom from progression is measured form the time of study entry to the progression of disease. Other causes of treatment failure as noted above in

time to treatment failure are not included in freedom from progression. This end point pertains to the control of disease.

9.10 Quality of life (QoL) assessments.

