10.4 Scheduled Assessment of Safety

- 10.4.1 Safety Data: Safety data will be collected on Day 1 of each cycle of chemotherapy and then at 3 month intervals for a total of 24 months. Analysis will also include MUGA scan studies done at baseline.
- 10.4.2 Efficacy endpoints: Efficacy endpoints data will be analyzed (primarily: CT scans and PET scans) at baseline and after 3 cycles of the above regimen and at completion of chemotherapy; and then every 3 to 6 months for 2 years total.

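### 2-year PFS is counted from registration but follow-up CTs are counted from the last dose, so no scan is fixed at month 24 and no planned analysis allows for the detection lag

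*Combined protocol and SAP*

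**What the plan says.** Section 2.2(c) makes the 2-year PFS rate a secondary objective. Section 9.3.5 gives it a powered exponential Wald test of 45% against 65% at one-sided 0.08. PFS there is "defined as the time from registration to the earlier of disease progression or death from any cause without documentation of disease progression". Section 9.3.6 adds Kaplan-Meier estimation.

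Imaging after treatment is set by Table 4 footnote 13: a scan 30 days after the last dose, and then "Thereafter, the follow-up schedule will be office visits with blood tests q 3 months and re-staging CTs q 6 months for 3 years". Patients who stop early for adverse events or progression follow the same calendar. Appendix VIII also has 6-monthly response assessments for 3 years after therapy. Section 10.4.2 differs, with efficacy data "and then every 3 to 6 months for 2 years total".

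Section 9.8.1 leaves the progression date open. It may be the first documentation of a new or larger lesion, "or the date of the scheduled clinic visit immediately after radiologic assessment has been completed". Section 9 contains no interval-censored or other analysis of detection delay.

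**The concern.** A progression that arises after the last scan before month 24, and is found only at the next scan, counts as progression-free at 2 years. The size of that gap depends on when the patient stopped treatment, because the stop date sets the scan dates. The comparison is with a fixed historical 45%, so the delay favours the regimen. The exponential test is affected as well as the month-24 estimate: late dating adds follow-up time to each event and lowers the estimated hazard. The clinic-visit option in 9.8.1 can only move events later.

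**Working it through.** **The plan's own figures.** The hazard is λ = −ln(S₂)/2, where S₂ is PFS at 2 years. This gives 0.399 per year for 45% and 0.215 for 65%. The medians ln2/λ are 1.74 and 3.22 years and agree with 9.3.5. Expected events under 65% with 15 months of accrual and 3 years of follow-up are 45 × [1 − (e^(−3λ) − e^(−4.25λ))/(1.25λ)] = 24.3. Power on the log-hazard scale is Φ(0.617 × √24.3 − 1.405) = 0.949. The stated values of about 20 events and 90% power reproduce with 2 years of follow-up instead (19.4 events, 90.5%). That mismatch is a separate matter, and the point below does not depend on it.

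**Scan dates.** Day 0 is taken as both registration and first dose, with no delays unless stated. From 5.1, 5.3 and 5.4.2, lead-in doses are on days 0 and 21 and AVD starts on day 42. AVD cycle 3 day 15 is day 112, and the last AVD dose is day 196. Consolidation doses are on days 210, 231, 252 and 273. The first post-treatment scan is at last dose + 30 days, and later scans follow every 182.6 days. Month 24 is day 730.5, with 30.44 days per month.

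**Reading at month 24** if every progression is found only by scan: S₂^(t/24), where t is the last scan month at or before 24.

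| Course | Last dose (day) | Last scan before month 24 | t | True 45% reads | True 65% reads |
|---|---|---|---|---|---|
| Full, on time | 273 | 303 + 2×182.6 = 668 | 22.0 | 48.2% | 67.4% |
| 6 AVD, no consolidation | 196 | 226 + 2×182.6 = 591 | 19.4 | 52.4% | 70.6% |
| 3 AVD + 4 consolidation doses | 189 | 219 + 2×182.6 = 584 | 19.2 | 52.8% | 70.9% |
| 3 AVD only | 112 | 142 + 3×182.6 = 690 | 22.7 | 47.0% | 66.5% |
| Stop after AVD cycle 4 | 140 | 170 + 3×182.6 = 718 | 23.6 | 45.6% | 65.5% |
| Full, consolidation begun 8 weeks after AVD | 315 | 345 + 2×182.6 = 710 | 23.3 | 46.1% | 65.8% |

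Stopping after AVD cycle 5 day 1 (day 154) puts a scan at 184 + 3×182.6 = day 732, at month 24 to within the ±2-day window. A true 45% then reads 45% if that scan falls just before month 24. If it falls just after, the previous scan at about month 18.0 governs and the reading is about 55%.

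**Half of events dated exactly** (an assumption covering deaths and clinically evident progression). The full-course reading is 0.5 × 48.2 + 0.5 × 45 = 46.6%. For a true 65% it is 0.5 × 67.4 + 0.5 × 65 = 66.2%.

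**The Wald test.** Simulation at a true 45%: 45 patients, uniform entry over 15 months, 3 further years of follow-up, full-course calendar. The statistic is √D × ln(λ̂/0.399), with λ̂ = events D divided by total time, rejecting below −1.405. The log-hazard scale is an assumption, since 9.3.5 names none.

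| Share of events found only by scan | Planned test, current calendar | Planned test, scans at months 12, 18, 24 … from registration |
|---|---|---|
| None | 0.07 | 0.07 |
| Half | 0.12 | 0.12 |
| All | 0.20 | 0.19 |

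An interval-censored exponential likelihood, with scan-found progressions placed between the last clear scan and the detecting scan, brings rejection back to about 0.07 under both calendars.

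**The case against.** The strongest reply is that the upper bounds assume something the plan does not. Footnote 13 requires 3-monthly visits, and Table 4 attaches physical examination, tumour measurement by examination and blood tests to them. Deaths count as PFS events and are dated exactly. The half-and-half shift of 1 to 2 points is small beside a standard error of about √(0.45 × 0.55/45) = 7 points. The historical 45% may carry a similar lag, PFS is secondary, and there is no second arm to bias. All of this stands, and it limits the size. It does not remove the direction of the error or the inflation of the test.

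Four stronger readings are tempting, and the documents do not support them:

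- *No patient is scanned at month 24.* Some stop dates and delays put a scan there. What is missing is a fixed one.
- *Early or frail stoppers always have the longer lag.* Three AVD cycles alone leaves a last scan at 22.7 months and delayed consolidation one at 23.3, both later than the on-time full course at 22.0.
- *PFS comparisons by CIRS or early response mainly compare scan timing.* Stop date may relate to both, but the lag does not run one way and no such effect has been computed.
- *Scans should be re-anchored to registration.* The inflation comes from 6-monthly detection, and rejection stays at 0.12 to 0.19. With a ±2-day window about half of the month-24 scans fall just after the landmark. With all events scan-detected, a true 45% would then read about (45 + 54.9)/2 = 50%, no better than the current full-course reading.

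Nor are on-treatment scans evenly spaced for everyone. Section 5.2.8.1 says "Patients 23 through 45 are not required to have a restaging PET or CT scan after the first 2" lead-in cycles, so the first required scan for those patients is at about week 17.

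**Conclusion.** The point holds in this form: the PFS clock and the scan clock differ, the gap before month 24 varies with the stop date, and the planned analyses ignore it. For the courses tabulated, the bias in 2-year PFS at a true 45% ranges from under 1 point to about 8 points as an upper bound. It is about 3 points for an on-time full course, or 1 to 2 if half of events are dated exactly. The one-sided 0.08 test has a real level of about 0.12 to 0.20 when half to all events are scan-detected. These figures rest on exponential PFS, on-time treatment except where stated, and an assumed share of scan-detected events that the documents do not give. This is a worthwhile, low-cost correction to a powered secondary endpoint, and no threat to the primary analysis.

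**What to change.** 1. In 9.3.5 and 9.3.6, add an interval-censored analysis for both the 2-year PFS estimate and the exponential test against 45%. Each scan-found progression lies between the last progression-free scan and the detecting scan. Deaths and clinically dated progressions stay exact.
2. In 9.8.1, date progression at the scan or biopsy that first documents it, and delete the option of using the following clinic visit.
3. Reconcile 10.4.2 with Table 4 footnote 13 and Appendix VIII, so that the interval and duration of follow-up imaging are stated once.

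No new visits or scans are needed, and re-anchoring scans to registration should not be required. The cost is one added analysis, a short amendment, and probably a slightly less favourable PFS figure.

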8.1.6.1 Reconstitution

Calculate the dose (mg) and number of vials of brentuximab vedotin required. The dose for patients with a weight of >100 kg should be calculated for 100 kg. Reconstitute each 50 mg vial of brentuximab vedotin with 10.5 mL of Sterile Water for Injection, USP, to yield a single-use solution containing 5 mg/mL brentuximab vedotin. Direct the stream toward wall of vial and not directly at the cake or powder. Gently swirl the vial to aid dissolution. DO NOT SHAKE. Inspect the reconstituted solution for particulates and discoloration. The reconstituted solution should be clear to slightly opalescent, colorless, and free of visible particulates. Following reconstitution, dilute immediately into an infusion bag, or store the solution at 2-8°C (36-46°F) and use within 24 hours of reconstitution. DO NOT FREEZE. Discard any unused portion left in the vial.

8.1.6.2 Dilution

Calculate the required volume of 5 mg/mL reconstituted brentuximab vedotin solution needed and withdraw this amount from the vials. The dose for patients with a weight of >100 kg should be calculated for 100 kg. Immediately add the reconstituted solution to an infusion bag containing a minimum volume of 100 mL to achieve a final concentration of 0.4 mg/mL to 1.8 mg/mL brentuximab vedotin. Brentuximab vedotin can be diluted into 0.9% Sodium Chloride Injection, 5% Dextrose Injection or Lactated Ringer's Injection. Gently invert the bag to mix the solution. Brentuximab vedotin contains no bacteriostatic preservatives. Following dilution, infuse the brentuximab vedotin solution immediately, or store the solution at 2-8°C (36-46°F) and use within 24 hours of reconstitution. DO NOT FREEZE.

8.1.7 **Administration. Study treatment must not be administered as an IV push or bolus.** Study treatment will be administered by outpatient IV

infusion given over approximately 30 minutes on Day 1 of each 21-day cycle. For this “lead in” phase, there are a total of 2 doses/cycles. In the absence of infusion toxicities, the infusion rate for all patients must be calculated in order to achieve a 30-minute infusion period. Study treatment will be administered through a dedicated IV line and cannot be mixed with other medications.

- **Avoid use in patients with severe renal impairment**
- **Avoid use in patients with moderate or severe hepatic impairment.**

Required Premedication and Postmedication. Routine premedication is not mandated prior to the first dose of study treatment. However, patients at clinical risk of nausea or who experience a Grade 1 or Grade 2 infusion-related reaction may receive subsequent study treatment with premedication as described below (e.g., prochlorperazine, ondansetron, etc).

8.1.8 **Incompatibilities.** No other anti-cancer treatment will be permitted during the treatment period, including chemotherapy, investigational therapies, radiation, biological response modifiers, hormone therapy, or immunotherapy.

8.1.9 **Compatibilities.** Best supportive care is expected. All concomitant medications and blood products administered during the patient’s participation in the study from the time of informed consent through the End of Treatment visit or 30 days after the last dose, whichever is later, must be recorded in the source document and on the CRF. Supportive measures consistent with optimal patient care should be provided throughout the study according to institutional standards.

8.1.10 **Availability.** This study drug will be supplied by Seattle Genetics. Drug orders should be emailed to Seattle Genetics drug supply at [contact] or faxed to [contact].

8.1.11 **Side effects.** In the initial SGN-35 phase I dose escalation study (administered once every 3 weeks) for patients with relapsed or refractory CD30-positive lymphomas (73% of patients had received prior autologous stem cell transplant), besides lymphocytopenia (47%) and neutropenia (16%), the incidence of grade 3/4 laboratory abnormalities was $\leq 15\%$. Thirty-one percent experienced SGN35-related therapy delay, primarily

neutropenia seen at higher doses. The dose limiting toxicities were neutropenic fever (prostatitis), hyperglycemia, and unrelated acute renal failure, which were seen at the SGN35 dose of 2.7 mg/kg.

Following are some of the side effects noted:

Likely (>20%): diarrhea, nausea, fatigue, fever, upper respiratory infection, decreased neutrophil count, peripheral sensory neuropathy.

Less Likely (<=20%): Allergic reaction; Cough, Dyspnea; Anxiety; Depression; Insomnia; Anemia; Blood and lymphatic system disorders - Other (lymphadenopathy); Dry skin; Alopecia, Hyperhidrosis; Dyspepsia; Abdominal pain; Constipation; Vomiting; Chills, Edema; Pain in administration site; Hyperhidrosis; Infections and infestations - Other (herpes zoster); lung infection; decreased WBC and platelet count; Musculoskeletal and connective tissue disorder - Other (muscle spasms); Pain(back, bone, extremity); Arthralgia; Myalgia; Weight loss; Anorexia; Pruritus; Maculo-papular rash; Dizziness; Headache; Paresthesia; Peripheral motor neuropathy;

Rare but Serious (<3%):Anaphylaxis; Pancreatitis; Hepatobiliary disorders - Other (hepatotoxicity); Respiratory, thoracic and mediastinal disorders - Other (pulmonary toxicity); Nervous system disorders-other(progressive multifocal leukoencephalopathy); Stevens Johnson Syndrome; Toxic epidermal necrolysis ;Tumor lysis syndrome .

Also Reported on SGN-35 Trials But With the Relationship to SGN-35 Still Undetermined: Acute kidney injury; Adult respiratory distress syndrome; Alanine aminotransferase increased; Aspartate aminotransferase increased; Dehydration; Encephalopathy; Generalized muscle weakness; Hot flashes; Hyperkalemia; Hypertension; Hypocalcemia; Hypophosphatemia; Hypotension; Infections and infestations - Other (oral candidiasis); Investigations - Other (blood LDH increased); Lymphocyte count decreased; Meningitis; Myelodysplastic syndrome; Myositis; Neck pain; Non-cardiac chest pain; Pericardial effusion; Pharyngitis; Pleural effusion; Pneumothorax; Productive cough; Renal and urinary disorders - Other (Pyelonephritis); Reproductive system and breast disorders - Other (groin pain); Respiratory, thoracic and mediastinal disorders - Other (oropharyngeal pain); Sinus tachycardia; Sinusitis; Skin infection; Syncope; Urinary tract infection

Please refer to current Investigator's brochure for detailed information on all side effects.

- 8.1.12 **Nursing/patient implications.** Please see above under administration in Section 8.1.7. In addition, avoid the use of SGN35 in patients with moderate (Child-Pugh B) or severe (Child –Pugh C) hepatic impairment. Regarding management of infusion reactions, infusion-related reactions

may occur during the infusion of study treatment. The infusion is to be administered at a site properly equipped and staffed to manage anaphylaxis should it occur. The patient should be observed for at least 60 minutes following the first infusion of study treatment. During this observation period, the IV line should remain open for at least 1 hour to allow administration of IV drugs if necessary. All supportive measures consistent with optimal patient care will be given throughout the study according to institutional standards. This includes adjusting the infusion time if necessary. Medications for infusion-related reactions, such as epinephrine, antihistamines, and corticosteroids, should be available for immediate use.

Patients who experience a Grade 1 or Grade 2 infusion-related reaction may receive subsequent study treatment infusions with premedication consisting of acetaminophen (650 mg orally) and diphenhydramine (25–50 mg orally or 10–25 mg IV) or according to institutional standards, administered 30–60 minutes prior to each 30-minute infusion.

8.2 Doxorubicin.

- 8.2.1 **Other names.** Adriamycin, Rubex, Adriamycin RDF, Adriamycin PFS, hydroxydaunorubicin, hydroxydaunomycin, ADR.
- 8.2.2 **Classification.** Anthracycline antibiotic.
- 8.2.3 **Mode of Action.** Intercalation between adjoining nucleotide pairs in the DNA helix causes inhibition of DNA and DNA-dependent RNA synthesis. Free radical generation is responsible for cardiac toxicity. Doxorubicin also inhibits topoisomerase II.
- 8.2.4 **Storage and stability.** Rubex or Adriamycin RDF intact vials are stable protected from light at room temperature. Adriamycin PFS vials must be refrigerated. Reconstituted solutions are stable for 24 hours at room temperature and 48 hours under refrigeration. The Adriamycin RDF 150 mg multidose vial is stable after reconstitution for 7 days at room temperature or 15 days if refrigerated and protected from sunlight.
- 8.2.5 **Dose specifics.** Doxorubicin will be given intravenously at a dose of 25 mg/m² on days 1 and 15 of each AVD chemotherapy cycle. A cycle will be repeated every 28 days. Use actual weight to calculate body surface area

and doses. See section 5.3.3 regarding dose modifications (toxicity-related).

- 8.2.6 **Preparation.** Add 5, 10, 25, 50, or 75 ml of preservative-free normal saline to the 10, 20, 50, 100, or 150 mg vial to produce a solution containing 2 mg/ml.
- 8.2.7 **Administration.** Intravenously as a bolus injection. Peripheral vein administration is allowed.
- 8.2.8 **Incompatibilities.** Physically incompatible with heparin, fluorouracil, aminophylline, cephalothin, dexamethasone, diazepam, hydrocortisone, and furosemide.
- 8.2.9 **Compatibilities.** Stable with vincristine in normal saline for 5 days at room temperature protected from light. Also compatible in solution with cyclophosphamide.
- 8.2.10 **Availability.** Commercially available as powder for injection in 10, 20, 50, 100, 150 mg vials, and as 2 mg/ml solution for injection in 10, 20, 50, and 200 mg vials.
- 8.2.11 **Side effects.** Hematologic: Leukopenia (dose-limiting), also thrombocytopenia and anemia. Nadir 10-14 days, recovery in 21 days. Dermatologic: Alopecia, usually complete; hyperpigmentation of nail beds and dermal creases; radiation recall. Gastrointestinal: Nausea and vomiting, sometimes severe; anorexia, diarrhea; mucositis, especially with daily x 3 schedule. Cardiovascular: Arrhythmias, ECG changes; rarely sudden death. Congestive heart failure due to cardiomyopathy related to total cumulative dose; risk is greater with total doses > 550 mg/m², mediastinal irradiation pre-existing cardiac disease, advanced age; risk is reduced with weekly or continuous infusion regimens. Other: Red discoloration of urine; fever; anaphylactoid reaction; may enhance cyclophosphamide cystitis or mercaptopurine hepatotoxicity. Local effects: Vesicant if extravasated; flush along vein, facial flush.
- 8.2.12 **Nursing/patient implications.** Monitor CBC, platelet counts. Vesicant - do not extravasate. Refer to extravasation protocol if inadvertent infiltration

occurs. Advise patient of alopecia. Instruct on how to obtain wig, hairpiece, etc. Hair loss generally occurs 2-4 weeks after injection and is usually complete. Advise patient of red discoloration of urine for 24 hours after administration of the drug. Administer antiemetics as indicated. Assess for stomatitis and treat symptomatically. Generally occurs 7-10 days after injection. Be aware of "Adria" flare - most common reaction consists of an erythematous streak up the vein. It is associated with urticaria and pruritus. Occasionally the use of corticosteroids and/or antihistamines has been useful. Monitor for signs and symptoms of cardiomyopathy. Calculate total cumulative dose with each administration.

8.3 Vinblastine.

- 8.3.1 **Other names.** Velban, vinblastine sulfate, vincaleukoblastine, VLB, Velsar, Alkaban AQ.
- 8.3.2 **Classification.** Vinca alkaloid (tubulin inhibitor).
- 8.3.3 **8.3.3 Mode of Action.** Vinblastine binds to tubulin, a protein that forms microtubules, thus interfering with spindle formation during metaphase and causing cessation of cellular mitosis.
- 8.3.4 **Storage and stability.** Drug vials are stored in the refrigerator. Reconstituted vinblastine, 1 mg/ml, is stable for 30 days in the refrigerator. Further diluted to a concentration of 0.01 mg/ml in normal saline or 5% dextrose, vinblastine is stable for 24 and 72 hours, respectively, at room temperature.
- 8.3.5 **Dose specifics.** Patients will receive Velban intravenously at a dose of 6 mg/m² on days 1 and 15 of each AVD chemotherapy cycle. A cycle will be repeated every 28 days. Use actual weight to calculate body surface area and doses. See section 5.3.3 regarding dose modifications (toxicity-related).
- 8.3.6 **Preparation.** The 10 mg vial is reconstituted with 10 ml of bacteriostatic normal saline, yielding a concentration of 1 mg/ml. Doses for continuous infusion may be further diluted with 50 ml or more of normal saline or 5% dextrose in water.

- 8.3.7 **Administration.** Intravenously as a bolus injection.
- 8.3.8 **Incompatibilities.** Furosemide, heparin; Infusaid pumps.
- 8.3.9 **Compatibilities.** Vinblastine is physically stable in normal saline solutions for at least 5 days, alone or mixed with doxorubicin, at 8, 25, and 32°C. Vinblastine is also compatible in solution with metoclopramide and bleomycin.
- 8.3.10 **Availability.** Vinblastine is commercially available in 10 mg vials, as a lyophilized powder and as a 1 mg/ml solution.
- 8.3.11 **Side effects.** Hematologic: Leukopenia, thrombocytopenia, anemia. Dermatologic: Alopecia, epilation; skin and soft tissue damage if extravasated (the manufacturer recommends subcutaneous injection of hyaluronidase and application of heat to help disperse the drug); rash, photosensitivity. Gastrointestinal: Nausea, vomiting (preventable); constipation (see neurological side effects); abdominal pain (cramps), anorexia, diarrhea, mucositis, gastrointestinal hemorrhage. Neurologic: Peripheral neuropathy (loss of deep tendon reflexes, paresthesias, paralysis); autonomic neuropathy (constipation, paralytic ileus, urinary retention, orthostasis); vocal cord paralysis; myalgias; Raynaud's phenomenon; headache, seizures, depression, dizziness, malaise; may be enhanced by concomitant use of interferon. Pulmonary; Bronchospasm (acute shortness of breath), more common when administered with mitomycin; pulmonary edema. Other: Severe pain in the jaw, pharynx, bones, back or limbs following injection; syndrome of inappropriate antidiuretic hormone (SIADH); fever; ischemic cardiotoxicity; enhanced interferon toxicity.
- 8.3.12 **Nursing/patient implications.** Premedicate with antiemetics as needed. Administer by slow IV push. Vesicant - do not extravasate. Refer to extravasation protocol if inadvertent infiltration occurs. Assess for neurotoxicity. Assess for constipation. Monitor CBC and platelet count.

8.4 Dacarbazine.

- 8.4.1 **Other names.** DTIC, DTIC-Dome,, DIC, imidazole carboxamide, dimethyl triazeno imidazole carboxamide.
- 8.4.2 **Classification.** Alkylating agent.
- 8.4.3 **Mode of Action.** Activity may be the result of at least 3 mechanisms: 1) alkylation; 2) antimetabolite activity as a purine precursor; and 3) interaction with sulfhydryl (SH) groups in proteins. Dacarbazine appears to be more active in G2 phase but is not particularly cell cycle phase specific.
- 8.4.4 **Storage and stability.** Store vials under refrigeration and protected from light. In solution, dacarbazine is stable for 96 hours if refrigerated and protected from light, 24 hours if not refrigerated but protected from light. When further diluted in 500 ml D5W or NS, it is stable for 24 hours if refrigerated, and 8 hours at room temperature and protected from light. Photodegradation: The manufacturer of dacarbazine states that the drug does not decompose when left at room temperature under normal lighting conditions for eight hours.
- NOTE:** A change in color of solution from pale yellow to pink is indicative of decomposition of the drug.
- 8.4.5 **Dose specifics.** Patients will receive Dacarbazine intravenously at a dose of 375 mg/m² on days 1 and 15 of each cycle of AVD chemotherapy. Cycles will be repeated every 28 days. Use actual weight to calculate body surface area and doses. See section 5.3.3 regarding dose modifications (toxicity-related).
- 8.4.6 **Preparation.** Dilute the 100, 200, and 500 mg vials with 9.9, 19.7, and 49.5 ml of sterile water, respectively, resulting in a concentration of 10 mg/ml. Protect the drug from direct light. Do not freeze. Discard if solution turns pink/red. The drug can be further diluted in 50-500 ml of 5% dextrose or normal saline.
- 8.4.7 **Administration.** Usually administered by intravenous infusion over 30 minutes or longer; has also been given IV push.

- 8.4.8 **Incompatibilities.** Metabolism of dacarbazine may be induced by phenytoin or phenobarbital. Toxicity may be enhanced if given concomitantly with allopurinol, azathioprine, or mercaptopurine. Dacarbazine is physically incompatible with hydrocortisone sodium succinate and heparin.
- 8.4.9 **Availability.** Commercially available in vials containing 100 mg, 200 mg, or 500 mg of lyophilized drug.
